3.4.2 Summary of Current Study Design (as of Amendment 12/07/2022)

For the Dose Expansion Cohort 2 Arm 3, treatment will be administered as outpatient for all cycles unless decided otherwise by the principal investigator based on clinical judgment. The standard treatment cycle will be 28 days (4 weeks). Reported adverse events and potential risks are described in Section 14. Appropriate dose modifications are described in Section 3.5. No investigational or commercial agents or therapies other than those described below may be administered during the study therapy period with the intent to treat the patient's malignancy. See **Table 4** below for description of drug regimen.

A cycle may be delayed for the following reasons:

- Scheduling or other administrative reasons (no more than 14 days)
- Administration of COVID-19 vaccination (if the delay would not result in more than 6 weeks treatment-free period)
- Toxicity/dose management as defined below

Table 4: Drug Regimen

Agent	Premedications; Precautions	Dose	Route	Schedule
Lenalidomide	Aspirin for thrombosis prophylaxis	As per dose level***	Oral	Days 1 to 10
Romidepsin	Premedicate with ondansetron or granisetron *	12mg/ m ² in 500 mL NS	IV over 4 hours	Days 1 and 10 (± 2 days)
CC-486 (5-azacitidine)	Premedicate with ondansetron or granisetron **	300mg	Oral	Days 1 to 10
Dexamethasone	No premedication	40mg	Oral	Days 1 and 10 (± 2 days)

* Mandatory for the first cycle; subsequently based on clinical judgement
** Not mandatory, administer based on clinical judgement
*** Doses as appropriate for assigned dose level

For a full detailed product description and administration guidelines, see Section 14. Infusions may be done peripherally or via central venous access device (if present; not required to be placed by the study).

NOTE: Cycles beyond Cycle 1 may not commence until the laboratory criteria in Section 2.1.1.8 are met and non-laboratory treatment-emergent AEs have resolved to grade ≤2 (grade ≤1 if at related to treatment).

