3.5.1 Treatment modifications for adverse reactions

All treatment modifications should be discussed with the senior clinical investigators on the study. Treatment modifications will follow the guidelines outlined in [Table 6](#). Any given dose modification after Cycle 1 can be repeated twice in a patient as long as the patient is benefiting from therapy and does not meet off-treatment criteria.

If a toxicity which requires modification of therapy per [Table 6](#) occurs during the window period (day -7 to day -1) and does not meet the definition of a DLT, cycle 1 day 1 may start after resolution to grade ≤ 1 (grade ≤ 2 for anemia).

All grading scales in the following tables are according to the revised NCI Common Terminology Criteria for Adverse Events (CTCAE) version 5.0.

Table 6: Dose Modification of Lenalidomide, romidepsin and CC-486 (5-azacitidine) for treatment related AEs

Event	Initial management	Follow-up Management
Cycle 1 DLT Evaluation Period		
Grade 1 AEs		
Any AE	Continue treatment	Continue monitoring and laboratories at least once weekly
Grade 2 AEs		
ANC: $<1.5 - 1.0 \times 10^9/L$	Continue treatment	Monitor cell counts at least twice weekly Pegfilgrastim*

Event	Initial management	Follow-up Management
Platelet: < 75,000 - 50,000/mcL	Consider holding treatment for up to 7 days	Monitor cell counts at least twice weekly Restart treatment when platelet count >75,000/mcL
Hgb: < 10.0 - 8.0g/dL	Continue treatment	Monitor cell counts at least twice weekly Consider transfusion before cycle 2
Any other AE	Continue treatment	Continue monitoring and laboratories once weekly
Grade 3 AEs		
ANC: <1.0 -0.5 x 10⁹/L	Hold treatment for up to 7 days Restart treatment at full doses	Monitor cell counts at least twice weekly G-CSF# and Pegfilgrastim*;
Platelet: <50,000 - 25,000/mcL	Hold treatment for up to 7 days Restart treatment at when platelets > 75,000/mcL	Monitor cell counts at least twice weekly If platelets are not > 75,000/mcL the patient is off treatment DLT
Hgb < 8.0g/dL	Hold treatment for up to 7 days Restart treatment after transfusion	Monitor cell counts at least twice weekly Transfusion until Hgb > 9 g/L
Any other AE	Hold treatment for up to 7 days Restart treatment when AE has resolved to ≤ grade 1	Continue monitoring and laboratories at least twice weekly If the AE has not improved to ≤ grade 1, the patient is off treatment DLT
Grade 4 AEs at any time during cycle 1		
Any AE	Discontinue treatment	Off treatment DLT
Cycles 2 through 6		

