Event	Initial management	Follow-up Management
Grade 1 AEs		
Any AE	Continue treatment	Continue monitoring and laboratories at least once weekly
Grade 2 AEs		
ANC: <1.5 – 1.0 x 10⁹/L	Continue treatment	Monitor cell counts at least twice weekly
Platelets <75,000 to 50,000/mcL	Continue treatment	Monitor cell counts at least twice weekly
Hgb: < 10.0 – 8.0g/dL	Continue treatment	Consider transfusion before the start of next cycle
Any other AE	Continue treatment	Continue monitoring and laboratories at least twice weekly

Event	Initial management	Follow-up Management
Grade 3 AEs		
ANC: < 1.0 - 0.5 x 10 ⁹ /L Or	1st event: continue treatment	Monitor cell counts at least twice weekly and use G-CSF support for the remainder of current cycle and all future cycles
	2nd event: hold lenalidomide and 5-azacytidine for remainder of cycle; next cycle may resume once ANC is >1.0	Monitor cell counts at least twice weekly and use G-CSF support Dose reduce both 5-azacytidine and lenalidomide for the next cycle
	3rd event: hold lenalidomide and 5-azacytidine for remainder of cycle; next cycle may resume once ANC is >1.0	Monitor cell counts at least twice weekly and use G-CSF support 2nd dose reduction of 5-azacytidine and lenalidomide and consider dose reduction of romidepsin with the next cycle
	4th event: hold lenalidomide and 5-azacytidine for remainder of cycle	Off study treatment
Platelet: <50,000 - 25,000/mcL	1st event: hold lenalidomide and 5-azacytidine for remainder of cycle; next cycle may resume once platelets are >75,000/mcL	Dose reduce both 5-azacytidine and lenalidomide for the next cycle
	2nd event: hold lenalidomide and 5-azacytidine for remainder of cycle; next cycle may resume once platelets are >75,000/mcL	2nd dose reduction of both 5-azacytidine and lenalidomide for the next cycle; consider dose reduction of romidepsin
	3rd event: hold lenalidomide and 5-azacytidine for remainder of cycle	Off study treatment
Hgb < 8.0g/dL	Continue treatment and consider blood transfusion	Monitor cell counts at least twice weekly
Any other grade 3 AE at least possibly related to study treatment	1st event: hold study treatment for the remainder of the cycle	Continue monitoring and laboratories at least twice weekly 1st Dose reduction of 5-azacytidine and lenalidomide for the next cycle
	2nd event: hold treatment for the remainder of the cycle	2nd dose reduction of 5-azacytidine and lenalidomide and consider 1st dose reduction of romidepsin

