	3rd event: hold study treatment for the remainder of the cycle	Off study treatment
Grade 4 AEs		
ANC < 0.5 x 10 ⁹ /L or Platelets <25,000/mcL	1st event: hold study treatment for the remainder of the cycle; next cycle may resume once ANC is >1.0 and platelets are >75,000/mcL	Monitor cell counts at least twice weekly Dose reduce 5-azacytidine and lenalidomide next cycle Consider dose reduction of romidepsin

Event	Initial management	Follow-up Management
	2nd event: hold study treatment for the remainder of the cycle	Monitor cell counts at least twice weekly 2nd dose reduction of 5-azacytidine, lenalidomide with next cycle, 1st dose reduction of romidepsin
Hgb Life threatening	Discontinue treatment	Off treatment unacceptable toxicity
Any other AE	1st event: hold treatment 7 to 14 days 2nd event: discontinue treatment	Continue monitoring and laboratories at least twice weekly 1 to 2 dose level reduction of 5-azacytidine or lenalidomide or romidepsin for most likely causative agent or all 3 drugs Consider discontinuation of treatment Off treatment unacceptable toxicity

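### Cycles 2-6: Table 6 lets dosing resume in the same cycle, with no recovery grade, after an early first other-AE grade 4 event but not after a first other-AE grade 3 event

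*Combined protocol and SAP*

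**What the plan says.** Table 6 in section 3.5.1 sets the actions for treatment-related adverse events. For cycles 2 to 6 it has separate rows for neutrophils, platelets and haemoglobin, and one other-AE row at each grade.

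- **Other AE, grade 3, first event** (at least possibly related to treatment): "1st event: hold study treatment for the remainder of the cycle". The follow-up is "1st Dose reduction of 5-azacytidine and lenalidomide for the next cycle".
- **Other AE, grade 4, first event:** "1st event: hold treatment 7 to 14 days". The follow-up is "1 to 2 dose level reduction of 5-azacytidine or lenalidomide or romidepsin for most likely causative agent or all 3 drugs", and discontinuation is to be considered. A second event ends treatment.

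The grade 4 other-AE row does not say whether dosing may resume within the cycle, to what grade the event must have recovered, or in which cycle the reduction begins.

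Other parts of the plan do set recovery conditions. The grade 4 neutrophil/platelet row for cycles 2-6 holds treatment for the rest of the cycle and adds "next cycle may resume once ANC is >1.0 and platelets are >75,000/mcL". The cycle 1 row for other grade 3 events says "Restart treatment when AE has resolved to ≤ grade 1". Section 3.4.2 has a general note that cycles after the first may not start until the laboratory criteria are met and "non-laboratory treatment-emergent AEs have resolved to grade ≤2 (grade ≤1 if at related to treatment".

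**The concern.** One expects the action after a grade 4 event to be at least as cautious on every element as the action after a grade 3 event of the same kind, unless the plan says that a difference is intended. Here the hold after grade 3 runs to the end of the cycle, while the hold after grade 4 is a number of days that can end while the cycle's dosing days are still running. The one general recovery rule is tied to the start of a cycle, so it does not reach a restart within a cycle.

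Two investigators who both follow the table could therefore act in opposite ways. One would have to withhold all drug until the next cycle after a grade 3 event. The other could give drug again a week after a grade 4 event, and no text would require that the event has resolved. At stake are patient safety and whether the rule can be applied consistently. The rows apply to Arm 3 patients from cycle 2 onward.

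**Working it through.** The plan gives no figure for this point, so there is nothing to reproduce. The check compares the first possible dosing day under each row.

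**Inputs**
- Cycle length: 28 days (section 3.4.2).
- Lenalidomide and CC-486: days 1 to 10 (section 3.4.2, Table 4).
- Romidepsin and dexamethasone: days 1 and 10, each ±2 days, so the second dose falls on days 8 to 12 (Table 4).
- Missed oral doses are not made up (section 3.4.5). I assume that held doses are treated the same way.
- Hold lengths: Table 6, as quoted above.

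I also assume that the hold of *h* days is counted from onset day *d*, and that the next cycle starts on time.

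**Grade 3.** The hold runs to day 28, so the earliest dosing day is 28 + 1 = 29, whatever the onset day.

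**Grade 4.** Dosing may restart on day *d* + *h*. Oral drug remains in the same cycle if *d* + *h* ≤ 10. The second romidepsin/dexamethasone dose remains if *d* + *h* ≤ 12.

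With *h* = 7, the oral condition gives *d* ≤ 3 and the romidepsin condition gives *d* ≤ 5:

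| Grade 4 onset | Earliest dosing, 7-day hold | Compared with grade 3 (day 29) |
|---|---|---|
| Days 1, 2, 3 | Days 8, 9, 10 of the same cycle | 21, 20, 19 days sooner |
| Days 4-5 | Romidepsin/dexamethasone only, by day 12 | 29 − 12 = 17 days sooner if given on day 12 |
| Days 6-22 | Day 29 | Same |
| Days 23-28 | Days 30-35 | Later |

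With *h* = 14, the earliest restart is day 1 + 14 = 15, after the last dosing day. Onset on days 1-15 gives day 29, the same as grade 3. Onset on days 16-28 gives days 30-42, which is later. Grade 4 is never sooner.

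For holds in between, take the earliest onset, *d* = 1. Oral drug needs *h* ≤ 9, and the second romidepsin/dexamethasone dose needs *h* ≤ 11. The earlier restart therefore depends on a hold near the lower end of the permitted range.

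**Sensitivity.** If held doses were shifted instead of skipped, onset on days 1-10 would resume between day 1 + 7 = 8 and day 10 + 14 = 24, always before day 29. The assumption used above is the one that gives the smaller discrepancy. With the former 21-day cycle the same onset days (1-3, or up to 5 for romidepsin) come out sooner.

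**Recovery condition.** The grade 3 other-AE row names no recovery grade either, but its next dose is always at a cycle start, where section 3.4.2 applies. After a grade 4 event with onset on day 6 or later, the next scheduled dose is also at a cycle start, so the note applies there too. It fails to apply only to a restart within the cycle, which is the same situation in which grade 4 is re-dosed sooner.

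**The case against.** The strongest reply is that this is a corner case inside a row that is stricter overall. Much of that stands. A first grade 4 event calls for a reduction of one or two levels, which may cover all three drugs, and discontinuation must be considered. A first grade 3 event calls for one reduction of two drugs. Grade 4 ends treatment at the second event, grade 3 at the third. A reader might infer that the plan is generally more lenient after grade 4; the row does not support that.

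There are also safeguards. Section 3.5.1 calls Table 6 a set of guidelines and asks that modifications be discussed with senior investigators. Section 3.7 requires assessments before the day 10 romidepsin dose. Section 3.11.1 allows removal for unacceptable toxicity or by investigator decision. These make an unconsidered restart less likely, but none of them sets a condition for resuming within a cycle.

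The triggering event may also be uncommon. Table 5.1, for romidepsin plus lenalidomide, shows no grade 4 event among its liver, electrolyte and other toxicities. That is a two-drug regimen, so it indicates low frequency without giving a rate for this combination.

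A reader might see the same inversion in the blood-count rows, because the grade 3 platelet row has a final step ("3rd event: hold lenalidomide and 5-azacytidine for remainder of cycle", then off treatment) while the grade 4 neutrophil/platelet row ends at a second event. The documents do not support that reading. A third grade 4 count event is not addressed, which is different from being allowed to continue. Section 3.5.1 also limits how often any modification may be repeated. At the second event the grade 4 row is the stricter one: it holds all study treatment and requires a romidepsin reduction, where the grade 3 platelet row holds two drugs and only asks that a romidepsin reduction be considered.

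**Conclusion.** The point holds in a narrow form. For a first other-AE event in cycles 2-6, Table 6 permits dosing again on days 8-10 of the same cycle after a grade 4 event with onset on days 1-3. Onset on days 4-5 permits the second romidepsin/dexamethasone dose by day 12. A grade 3 event rules out dosing before day 29. In these cases no recovery grade applies to the grade 4 restart.

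This rests on a 28-day cycle, a hold near 7 days counted from onset, held doses not made up, and the next cycle starting on time. With a 14-day hold or later onset, grade 4 is not re-dosed sooner.

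A reader might go further and infer that the adverse-event frequencies, a primary endpoint, are distorted. The documents do not support that: the frequencies are descriptive summaries of the regimen as given, and no effect on them has been shown. Nor can these rows affect the MTD, which section 10.2 bases on cycle 1. The issue is a conflict between neighbouring rows on a safety action. That is more than a missing detail, and it should be corrected in the next amendment.

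**What to change.** Reconcile the grade 3 and grade 4 other-AE rows for cycles 2-6 with each other and with the note in section 3.4.2. For each grade, state:

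1. whether dosing may resume within the same cycle or only at the next one;
2. what recovery condition must be met before any resumption, including one within a cycle;
3. when the dose reduction takes effect.

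If a difference between the grades is intended, say so. The sponsor's clinicians decide which rule applies; this review takes no position on it.

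The cost is an edit to a few cells of Table 6 and, if needed, one sentence in section 3.4.2. It adds no patients or visits. Any effect on delivered dose depends on the rule chosen.

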3.5.2 Lenalidomide dose modifications for decreased creatinine clearance

For each cycle to commence, creatinine clearance must be > 60 mL/min/1.73 m² calculated by eGFR in the clinical lab per Section [2.1.1.8](#). For a decrease of creatinine clearance, which occurs during the cycle, the dose of lenalidomide will be modified per [Table 7](#). Decreases of creatinine clearance deemed treatment-related, may result in discontinuation of protocol therapy as per [Table 6](#).

Table 7: Lenalidomide renal dose adjustments

Creatinine clearance calculated by eGFR in the clinical lab	Lenalidomide dose	Lenalidomide schedule Days 1 to 10 (Day -7 to 10 for first cycle)
31-60 mL/min/1.73 m ²	Reduce by 50%	Daily
\leq 30 mL/min/1.73 m ²	Reduce by 50%	Every other day

3.6 PROTOCOL STOPPING RULE

In the event of patient death (grade 5) determined to be related to the investigational treatment, further enrollment will be halted, consideration will be given to discontinuing treatment for all active patients and suspension of the protocol until the exact cause of the death is fully understood and whether the protocol should be terminated.

3.7 ON STUDY EVALUATIONS

Prior to romidepsin administration (Day 1 and 10), pre-dose assessments must be performed (up to 3 days prior). After Cycle 1, pre-dose assessments may be performed up to 3 days prior to a cycle except where otherwise noted. The results from all procedures/tests must be reviewed prior to initiation of each cycle of treatment for consideration of dose modifications and delay of therapy.

Treatment with lenalidomide, romidepsin and CC-486 (5-azacitidine) will continue for six cycles or until disease progression, unacceptable treatment-related toxicity or other reasons outlined in Section 3.11.1.

Refer to the Study Calendar (Section 3.9) for a complete list of procedures to be performed at each scheduled study visit. See also Section 5 for all samples to be collected for correlative research. During treatment, it is expected that all laboratory and clinical assessments be conducted at the NIH (including post-treatment imaging evaluations); results from outside NIH will only be accepted at the discretion of the investigator.

NOTE: Recently a patient treated in this study had symptoms of an unusual very uncommon serious toxicity called rhabdomyolysis related to one of the study drugs which is damage to skeletal muscles that produces significant elevations in the serum of muscle enzymes like creatinine kinase or aldolase. If a patient experiences suspicious symptoms, or has physical exam findings suggestive of this toxicity, the patient will be evaluated clinically (e.g., blood and urine tests will be performed) at the direction of the Principal Investigator/treating investigator to determine if the patient is having this toxicity.

3.8 POST-TREATMENT EVALUATIONS

Patients who discontinue investigational therapy before completing protocol treatment due to disease progression will be followed clinically until completion of the Safety Follow-up Visit or until death, whichever occurs first. These patients will continue to be followed for overall survival as outlined Section 3.8.2. Patients removed from study treatment for unacceptable adverse event(s) will be followed until resolution or stabilization of the adverse event.

3.8.1 Safety Follow-Up Visit

The safety follow-up visit should occur 30 days (+7 days) after the last dose of trial treatment, or before the initiation of a new anti-cancer treatment, whichever comes first. Required testing is as noted in the Study Calendars (Section 3.9). All AEs that occur prior to the Safety Follow-Up Visit should be recorded. See section 6.1.1 for documentation of AEs after study treatment has ended.

3.8.2 Follow-Up Visits - Prior to Disease Progression

Patients who complete trial treatment without evidence of disease progression will move into the Follow-up Phase and may be assessed every 60 days (\pm 7 days) for 6 months; then every 90 days (\pm 14 days) for 2 years; then every six months (\pm 28 days) for 2 years, then annually (\pm 6 weeks) after finishing treatment by radiologic imaging or other clinical assessments to monitor disease status. Every effort should be made to collect information regarding disease status until the start of new anti-neoplastic therapy, disease progression, death, or end of the study. If the patient cannot return to the Clinical Center for any of these visits, a request will be made to have a local physician or laboratory collect a CBC with differential and send the results. If this is not possible, patients may be assessed by telephone or email for symptoms.

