3 STUDY IMPLEMENTATION

3.1 STUDY DESIGN

To determine the maximum tolerated dose (MTD), and the safety and toxicity profile of the combination of lenalidomide, CC-486 (5-azacitidine) and romidepsin in patients with refractory/relapsed TCM, a phase 1 open-label, non-randomized, single-center study will be conducted at the NCI. A standard “3 + 3” design will be used to determine the MTD of dose-escalated lenalidomide in combination with fixed doses of CC-486 (5-azacitidine), romidepsin (R) and dexamethasone (D) with an expansion cohort at the MTD.

In patients with relapsed or refractory TCM, lenalidomide will be administered by oral intake in a dose-escalation with a starting dose of 5mg daily, a second dose level of 10mg daily, a third dose level at 15mg daily, and a fourth dose level at 20mg daily on days -7 to day 10 of first cycle (see **Table 1** for additional dose levels and schedules, cycles are 21 days each). After the second cycle, lenalidomide will be given from day 1 to day 10 in each cycle for up to six cycles. CC-486 (5-azacitidine) with a dose of 300mg oral intake daily will be given on day 1 to day 10, romidepsin will be administered at a dose of 12 mg/ m² on days 1 and 10 (±2 days) and dexamethasone will be given on day 1 and 10 (±2 days) of the cycle.

After approval of Amendment 12/07/2022: Participants will receive six cycles (each 28 days in length) of: lenalidomide at the MTD from day 1 to day 10, CC-486 (5-azacitidine) at a dose of 300mg oral intake daily given on day 1 to day 10, romidepsin administered at a dose of 12 mg/ m² on days 1 and 10 (±2 days) and dexamethasone on day 1 and 10 (±2 days) of the cycle.

Treatment will continue for a maximum of 6 cycles or until toxicity (i.e., dose limiting toxicity) as found in Section 3.9 or toxicity requiring discontinuation as defined in Section 3.5) or progressive disease.

The treatment will be repeated for up to 6 cycles. The patients are allowed to proceed to stem cell transplantation (SCT) if eligible during and after the protocol treatment. Patients who undergo SCT before all 6 cycles of protocol treatment are administered will be taken off therapy. All patients who undergo SCT will continue to be followed for survival, but not for toxicity (see Section 3.8)

Cycles 1-6												28
Azacitidine												by mouth once per day
Lenalidomide												by mouth once per day
D												D
R												R

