3.8.3 Follow-Up Visits - Survival/Post-Disease Progression

Once a subject experiences confirmed disease progression or starts a new anti-cancer therapy, the subject moves into the survival follow-up phase and should be contacted (e.g., phone, email, etc.; in-person visit not required) at least every 3 to 6 months to collect information on new anti-cancer treatments received and to assess for survival status until death, withdrawal of consent, or the end of the study, whichever occurs first (see Study Calendar, Section 3.9). Any adverse events which

Abbreviated Title: RAdR for R/R TCM

Version Date: 12/04/2025

are present at the time of discontinuation should be followed in accordance with the safety requirements.

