¹ 30 days (± 7) following last dose of any study drug (via clinic or phone). If initiating new anti-cancer therapy within 30 days after last dose of any study drug, 30-day safety follow-up visit must occur before first dose of new therapy.

² Screening and Baseline evaluations should be performed within 28 days prior to enrollment and dosing, respectively, unless otherwise noted and with the following exceptions: Confirmation of diagnosis (no time limit); HIV antibody, HTLV-1/2 serologies, Hepatitis B surface antigen and Hepatitis C antibody, EKG, TTE, bone marrow aspiration/biopsy and Clonal T-cell receptor rearrangement by PCR (all within 3 months), baseline pregnancy testing (within 10 – 14 days and within 24 hours prior to prescribing lenalidomide) **NOTE:** Any screening tests performed within the specified time frame for baseline do not need to be repeated.

³ To be performed on Day 21 (± 2 days) of Cycles 2, 4, and 6. Confirmatory scans should also be obtained 4 weeks following initial documentation of objective response.

⁴ To be done at end of treatment (30 days after last dose of study treatment; may be combined with 30 day safety follow-up, if timing coincides). If subject to initiate new anti-cancer therapy assessments should occur before the first dose of the new therapy.

⁵ Follow-up to occur about every 60 days (± 7 days) for first 6 months, every 90 days (± 14 days) for 2 years, then every 6 months (± 28 days) for another 2 years and then annually (± 6 weeks) until disease progression or initiation of new anti-cancer therapy.

⁶ After disease progression or initiation of new anti-cancer therapy, contact for survival about every 3 to 6 months (± 4 weeks).

⁷ Pathologic review/confirmation of diagnosis by Laboratory of Pathology, NCI (no time limit). If archival sample is not available or not adequate, a fresh tumor biopsy and/or peripheral blood sample will be obtained.

⁸ Complete medical history at screening/baseline. Interim on study and in follow-up. Disease and social history required only at screening.

⁹ Physical exams to include vitals, weight, and height (screening only).

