		Baseline ⁴ (C1 D-7)	C1 D1	C1 D10	C1 D15	C2-6 D1	C2-6 D10	Follow-up [#]	
Other Samples									
Germline DNA	• Blood, Buccal Swab, or Saliva (preferred) – see 5.4	X							Leidos CSL
(X) = Optional; samples will be collected if adequate time/staff available for processing, and if research blood drawn is less than the allowed limit noted in Section 5.1.3 . If an optional sample is not collected at baseline, it would also not be collected in follow-up unless specifically requested by the PI.									
[†] The location of specimen processing or analysis may be adjusted with the permission of the PI or laboratory investigator.									
*Tubes/media may be adjusted at the time of collection based upon materials available or to ensure the best samples are collected for planned analyses.									
** May be omitted if research blood drawn would be over the allowed limit noted in Section 5.1.3 .									
*** Tumor biopsy (bone marrow, skin, or ultrasound-guided LN biopsies) is required if archival tissue is not available or adequate; otherwise, this is optional									
[†] All time points during treatment are ± 3 days. All follow-up time points are ± 7 days.									
#Subjects who discontinue treatment for a reason other than disease progression and who do not start new treatment should continue to have study bloods collected at the scheduled time points.									
¹ At the end of treatment only.									
² At each follow-up visit prior to disease progression, as specified in Section 3.8.2 .									
⁴ With the exception of tissue immune cell subset (if applicable) and Germline DNA which are to be collected during Baseline, samples correlating to the lead-in window will no longer be collected as the lead-in window has been retired.									

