6.3.5 Progression-Free Survival

Progression-free survival (PFS) is defined as the duration of time from the date of study enrollment until time of disease relapse, disease progression, or death, whichever occurs first.

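### Sections 3.8.2 and 3.8.3 give patients who stop early without progression no follow-up schedule, in conflict with the Study Calendar, and relapse after transplant is not collected although PFS and DOR count it

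*Combined protocol and SAP*

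**What the plan says.** Section 3.8 and its subsections describe three ways off treatment.

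- **Stopped for progression.** Safety visit, then overall-survival follow-up. The text refers to 3.8.2 for this, although the survival section is 3.8.3.
- **Stopped for toxicity.** "Patients removed from study treatment for unacceptable adverse event(s) will be followed until resolution or stabilization of the adverse event".
- **Completed without progression.** "Patients who complete trial treatment without evidence of disease progression will move into the Follow-up Phase". Disease status is then sought on a schedule of every 60 days, then every 90 days, then less often. The aim is to "collect information regarding disease status until the start of new anti-neoplastic therapy, disease progression, death, or end of the study".

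Survival contact has its own trigger in 3.8.3: "Once a subject experiences confirmed disease progression or starts a new anti-cancer therapy, the subject moves into the survival follow-up phase".

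For transplant, section 3.1 says: "All patients who undergo SCT will continue to be followed for survival, but not for toxicity".

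Two other places set no completion condition. Footnote 5 of the Study Calendar (3.9) runs the pre-progression follow-up column "until disease progression or initiation of new anti-cancer therapy". A footnote to the sample table in 5.1.1 says that patients who stop for a reason other than progression, and start no new treatment, "should continue to have study bloods collected at the scheduled time points".

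PFS in 6.3.5 runs "until time of disease relapse, disease progression, or death, whichever occurs first". DOR in 6.3.3 likewise ends at documented recurrence, progression or death. Section 10.4.3 censors EFS, PFS, OS and DOR at the date of last follow-up.

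**The concern.** Section 3.11.1 lists several reasons for stopping besides completion and progression: unacceptable toxicity, intercurrent illness, the patient's request, the investigator's decision and non-compliance. A patient who stops for one of these, without progression and without new therapy, has not completed treatment and so does not meet the entry wording of 3.8.2. Nor does the patient meet the trigger in 3.8.3. Section 3.11 sends follow-up after treatment back to 3.8, so staff who look there find no schedule for this patient.

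PFS, DOR, EFS and OS are all secondary endpoints. If disease status stops being collected in patients who left because of toxicity, the loss may be related to outcome, and no censoring rule recovers a progression that was never recorded.

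Transplant matters separately because section 1.10.2 describes the regimen as induction and as a bridge to allogeneic transplant. Transplanted patients are therefore an expected and important group.

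**Working it through.** The plan gives no early-stop rate, no transplant rate and no figure for this point, so there is nothing of its own to reproduce. The check is mainly a comparison of passages.

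**Step 1: a patient who stops early without progression or new therapy.**

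| Place | Does it cover this patient? |
|---|---|
| 3.8, toxicity sentence | Only for the adverse event; silent on disease status |
| 3.8.2, entry wording | No: the patient did not complete treatment |
| 3.8.3, and calendar footnote 6 | No: the trigger is progression or new therapy |
| 3.9, discontinuation visit | Yes: one visit with imaging |
| 3.9, footnote 5 | Yes by implication: an end point, no completion condition |
| 5.1.1, footnotes | Yes for blood samples; the ctDNA footnote ties them to the 3.8.2 visits |
| 3.11.2, off-study criteria | Toxicity is not a reason to leave the study |

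The first three rows assign no follow-up for progression or survival. The last four assume that follow-up continues. Both cannot be followed.

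**Step 2: a transplanted patient.** Let SCT occur at time S, relapse at R after S, and the last survival contact with the patient alive at L after R. Suppose the relapse is not recorded, because 3.1 names survival only and 3.8.2 stops at new anti-neoplastic therapy.

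- PFS by 6.3.5: event at R.
- PFS by 10.4.3 read literally: censored at L. One event is lost and L − R of progression-free time is added.
- If the patient later dies at D: event at D instead of R, an excess of D − R.

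Both errors lengthen PFS. For DOR, 6.3.3 ends an uneventful response at the last assessment, whereas 10.4.3 uses the last follow-up, so the two sections give different dates for the same patient. This step also applies to completers who later go to transplant.

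**Step 3: illustration of Step 1 on assumed inputs.** PFS is exponential with a 4-month median (the romidepsin phase II figure in 1.6.1), so λ = ln 2 / 4 = 0.173 per month. Non-progression stopping has constant hazard g over 6 × 28 = 168 days (5.52 months). It is chosen so that g/(g + λ) × [1 − exp(−(g + λ) × 5.52)] equals 10% to 40%, an assumed range. Every stopper is censored 30 + 7 = 37 days after stopping, and the comparison is continued follow-up to 36 months (400,000 simulated patients).

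If stopping is unrelated to later PFS, the events seen are:

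| Stop early | Of 30 patients, 3.8 literal | Of 30, continued | Of 9 patients, 3.8 literal | Of 9, continued |
|---|---|---|---|---|
| 10% | 27.5 | 29.9 | 8.3 | 9.0 |
| 20% | 25.1 | 29.9 | 7.5 | 9.0 |
| 30% | 22.7 | 29.9 | 6.8 | 9.0 |
| 40% | 20.3 | 29.9 | 6.1 | 9.0 |

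Kaplan-Meier median in months, 3.8 literal against continued follow-up:

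| Hazard ratio after stopping | 10% stop | 40% stop |
|---|---|---|
| 0.5 | 4.06 vs 4.13 | 4.34 vs 4.78 |
| 1 | 3.99 vs 3.99 | 4.00 vs 4.00 |
| 2 | 3.90 vs 3.83 | 3.53 vs 3.35 |

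The largest shift is 4.78 − 4.34 = 0.44 months. It grows with the assumed median: at 8 months and 40% stopping it is 10.04 − 8.41 = 1.63 months (ratio 0.5) or 7.26 − 6.31 = 0.95 months (ratio 2). With a ratio of 1 there is no bias, only fewer events.

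**The case against.** A reader might infer that early stoppers and transplanted patients simply drop out of PFS, DOR and EFS. The documents do not support that.

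- Section 3.8.2 does not say that only completers are followed, and the toxicity sentence sets how long the adverse event is followed, not when disease follow-up ends.
- The calendar has imaging at treatment discontinuation, footnote 5 has no completion condition, and the sample table expects these patients at later visits. Neither a toxicity stop nor SCT is an off-study criterion. A site working from the calendar would probably keep following them.
- EFS after transplant need not be lost. Section 6.3.4 counts alternative anti-lymphoma therapy as an event. If SCT qualifies, the EFS event is already dated; the plan does not say whether it does.
- Deaths after SCT are still collected, so PFS is only partly affected. For CTCL patients, 6.3.1.2 uses the off-treatment date for time to progression and/or DOR, a different rule again from 6.3.3.
- These are secondary, descriptive Kaplan-Meier estimates in a phase 1 study.

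A reader might also try to size the group from the grade 4 haematological toxicity in Table 5.1. That table describes a two-drug regimen and is not limited to cycle 1. It also counts grade 4 lymphocytopenia, through which 3.2.1 continues treatment when it is asymptomatic. It cannot supply an early-stop rate for this trial.

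All of this stands, and it limits the point to a contradiction plus a missing transplant rule. It does not remove either. Footnote 5 gives timing and an end point without saying who enters, and the sample footnote promises blood draws, not disease assessment.

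**Conclusion.** The point holds as an inconsistency that needs correction. On the wording of 3.8, a patient who stops early without progression or new therapy has no assigned disease-status or survival follow-up, while 3.9 and 5.1.1 assume follow-up continues. If 3.8 is followed literally, PFS, DOR and possibly OS data are lost in a group selected partly by toxicity.

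Separately, relapse after SCT is not collected although PFS and DOR count it. Censoring at last follow-up can then credit unobserved progression-free time.

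The size is unknown. The illustration rests on an assumed stopping rate, exponential PFS and censoring of every stopper. Under a 4-month median it shows a modest shift in median PFS, at most about 0.4 months, and none if stopping is unrelated to outcome; the loss of events is more visible. It does not show that the estimates would be misleading in this trial. The correction should nevertheless be made, because missing progression dates cannot be restored at analysis.

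**What to change.** 1. **Section 3.8.2.** Replace the entry condition with: *All patients who stop trial treatment for any reason without disease progression and have not started new anti-cancer therapy*. This covers completers and agrees with calendar footnote 5 and the 5.1.1 footnote.
2. **Section 3.8.** State that follow-up of an adverse event to resolution is in addition to 3.8.2, and correct the overall-survival cross-reference from 3.8.2 to 3.8.3.
3. **Sections 3.1, 3.8.3, 6.3 and 10.4.3.** Choose one rule for SCT and other new therapy. Either record the date of first relapse or progression at the survival contacts already planned (every 3 to 6 months) and count it, or censor PFS and DOR at the last disease assessment before SCT or new therapy. In both cases state whether SCT is an EFS event, and make 6.3.3 and 10.4.3 agree on the DOR censoring date.

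The cost is protocol wording, a few extra visits on the existing schedule and, under the first option in item 3, one CRF field. No sample-size figure changes. Since 3.4.1 reports 20 patients already enrolled in escalation, the sponsor can also count those who stopped early without progression, which would replace the assumed range with the trial's own number.
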